11.8 Subgroup analysis

Analysis will be performed on subgroups of the population. Subjects will be classified into subgroups as follows:

11.8.1 Subjects with Anytriptan use within three months of screening:

Summary of Demographics and baseline characteristics for mITT Population, summary of Headache Pain for mITT population and summary of Most Bothersome symptom for mITT population tables will be provided. Additional tables that will be provided include summary of headache relief for ITT population and Incidence of Treatment-Emergent Adverse Events for safety population.

11.8.2 Subjects that dosed greater than 4 hours after migraine start:

The tables that will be provided include Summary of Demographics and Baseline Characteristics for ITT population, Summary of Headache Pain for ITT population, Summary of Most Bothersome Symptom for ITT population, and Summary of headache relief for ITT population.

11.8.3 Subjects with either Topamax or Propranolol use while on study:

The mITT population tables that will be included are Summary of Demographics and baseline characteristics for mITT population, Summary of headache pain for mITT population, and Summary of Most Bothersome symptom for mITT population. Additional tables will include Summary of Headache Relief for ITT population.

11.8.4 Subjects with Topamax use while on study:

The mITT population tables that will be included are Summary of demographics and baseline characteristics for mITT population, Summary of headache pain for mITT population, Summary of Most Bothersome symptom for mITT population. Additional tables will include Summary of headache relief for ITT population, Incidence of Treatment-Emergent Adverse Events for Safety population, and Incidence of Treatment-Emergent Adverse Events for Safety-2nd Dose population.

11.8.5 Subjects with propranolol use while on study:

The mITT population tables that will be included are Summary of Demographics and Baseline characteristics for mITT population, Summary of Headache Pain for mITT population, Summary of Most Bothersome Symptom for mITT population. Additional tables will include Summary of

Headache Relief for ITT population, Incidence of Treatment-Emergent Adverse Events for Safety Population, and Incidence of Treatment-Emergent Adverse Events for Safety-2nd Dose population.

11.8.6 Subjects with one or more CVRFs

The mITT population tables that will be included are Summary of Demographics and Baseline Characteristics for mITT population, Summary of Headache Pain for mITT population, Summary of Most Bothersome Symptom for mITT population. Additional tables include Summary of Headache Relief for ITT population, and Incidence of Treatment-Emergent Adverse Events for Safety Population. Cardiovascular risk factors considered are hypertension, hypercholesterolemia, smoker, obesity, diabetes, strong family history of coronary artery disease (CAD), female with surgical or physiological menopause and male over 40 years of age.

11.8.7 Subjects with TEAEs of dizziness:

The mITT population tables that will be included are Summary of Demographics and baseline characteristics for mITT population, Summary of headache pain for mITT population, and Summary of Most Bothersome symptom for mITT population. Additional tables will include Summary of Headache Relief, Summary of Patient Global Impression, and Summary of Disability for ITT population. Summary of Time-to-Onset and duration for First-Dose Treatment-Emergent Dizziness Relative to Dosing for Safety Population and safety-2nd dose population will be provided.

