This study is a Phase 3 multicenter study in subjects with acute migraine. The study is designed to determine the efficacy and safety of lasmiditan 200 mg compared to placebo and lasmiditan 100 mg compared to placebo given as a first dose for the treatment of a migraine attack. A second dose of study drug is included in the study design to investigate the safety and efficacy of lasmiditan 200 mg compared to placebo and lasmiditan 100 mg compared to placebo when taken for rescue or when taken for recurrence of migraine. In addition to safety assessments, information will be obtained on the different dose levels of lasmiditan. Patients with cardiovascular risk factors will be eligible to participate in this clinical trial. Data from this study

will be used to further investigate and confirm the safety and efficacy of lasmiditan in the treatment of acute migraine in patients with risk factors for cardiovascular disease.

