## 5.4 Safety objectives

To explore the safety and tolerability of lasmiditan 50 mg, of lasmiditan 100 mg and of lasmiditan 200 mg, as the first dose and as a second dose, in terms of adverse events (AEs), physical examinations, vital signs, clinical laboratory evaluations, and 12-lead electrocardiograms (ECGs).

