4.1 Subpopulations

The Safety-2nd Dose and ITT-2nd Dose populations will be further classified as rescue or recurrence populations. Subjects who took a second dose will be classified as either rescue or recurrence as follows:

- **Rescue:** subjects who did not achieve headache pain-free at 2 hours, completed the 2-hour assessments, and took a second dose of study drug between 2 hours and 24 hours post first dose.
- **Recurrence:** subjects who achieved headache pain-free at 2 hours, but then experienced recurrence of mild, moderate, or severe migraine pain and took a second dose of study drug up to 24 hours from the first dose.

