12 SAFETY ANALYSIS

This section details the specifications for summarizing safety endpoints.

Adverse event analyses will be presented on both the Safety and Safety-2nd Dose populations. Summaries on the Safety population will only include data up to the time of dosing with a second dose, and will be presented based on the first dose taken. Summaries on the Safety-2nd Dose population will only include data on or after the time of dosing with a second dose, and will be presented based on treatment sequence.

Laboratory, vitals, ECG, and C-SSRS analyses will be presented on the Safety population. These analyses will be presented by treatment sequence.

Safety endpoints will be summarized using descriptive or counts and percentages, as appropriate.

Values for all safety endpoints will also be presented in listings sorted by treatment group, site, and subject.

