12.1 Adverse Events

An adverse event (AE) with the date/time of onset, or that worsens in intensity, at or within 48 hours after the time of dosing with study drug will be considered a TEAE. AEs with a missing start date will be assumed to be treatment-emergent, except as described in Appendix 1. If a subject takes at least one dose of study drug, but the date and time of dosing is missing in the e-diary, all AEs for that subject will be considered treatment-emergent, if the AEs occur between available date of dosing as recorded only in CRF for up to 48 hours (2 days) post recorded date of dosing. If the date and time of the second dose is missing in e-diary then all AEs for that subject will be considered as treatment emergent due to second dose, if AEs occur between available date of dosing in CRF for second dose, and an ending boundary of 2 days after recorded date of dosing with second dose, inclusive. See Appendix 1 for derivations related to partial dates and times.

Nausea and/or vomiting reported as adverse events during a migraine by any subject that also noted these as characteristics of their migraine will be compared against placebo and may not be considered related to treatment but rather an underlying condition of the migraine.

AEs will be coded by the Medical Dictionary for Regulatory Activities (MedDRA) version 18.0.

Unless otherwise stated, frequencies of adverse events will be displayed by applicable treatment group and overall. AEs will be sorted alphabetically by system organ class (SOC) and then preferred term (PT) by frequency. For the overall summary of AEs, both subjects ever experiencing an event, as well as total events, will be presented. For all other summaries, subjects with multiple occurrences of the same AE preferred term will be counted once within the corresponding system organ class and preferred term.

Adverse events will be summarized in the following tables:

- Overall summary of AEs, including:
 - AEs
 - TEAEs
 - Related TEAEs
 - TEAEs leading to study discontinuation
 - Serious TEAEs
 - Related serious TEAEs
 - TEAEs leading to death
- Incidence of TEAEs
- Incidence of TEAEs by relationship to study drug
- Incidence of TEAEs by maximum severity
- Incidence of AEs leading to study discontinuation
- Incidence of related AEs leading to study discontinuation
- Incidence of TEAEs leading to death
- Incidence of serious TEAEs
- Incidence of serious TEAEs by relationship to study drug

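### The only adverse event table planned for subjects with cardiovascular risk factors stops at the second dose, so their events after redosing are never tabulated by risk-factor status

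*SAP*

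**What the plan says.** SAP 4.3 lists subjects with one or more cardiovascular risk factors as a planned subgroup, and SAP 11.8.6 names its tables. After the mITT tables it says: "Additional tables include Summary of Headache Relief for ITT population, and Incidence of Treatment-Emergent Adverse Events for Safety Population". That is the only adverse event output for the subgroup.

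SAP 12 sets the data window for that table: "Summaries on the Safety population will only include data up to the time of dosing with a second dose". Events from the second dose onward go to the Safety-2nd Dose summaries, presented by treatment sequence. Listings are sorted by treatment group, site and subject.

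For the Topamax and propranolol subgroups (SAP 11.8.4 and 11.8.5), the plan names the first-dose table and also "Incidence of Treatment-Emergent Adverse Events for Safety-2nd Dose population". For the triptan subgroup (SAP 11.8.1) it names only the "summary of headache relief for ITT population and Incidence of Treatment-Emergent Adverse Events for safety population", alongside the mITT tables.

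Protocol 5.4 sets a safety objective for each dose level both as first and as second dose. Protocol 4 states that patients with cardiovascular risk factors may enrol, and that data from the study "will be used to further investigate and confirm the safety and efficacy of lasmiditan in the treatment of acute migraine" in patients with such risk factors.

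**The concern.** Cardiovascular safety is central to the case for this drug: Protocol 4 presents it as an option for patients in whom triptans are contraindicated or used with caution. A reader of the study report will look for adverse event rates in subjects with risk factors, and the plan supplies them only up to redosing.

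The cut has two effects. Everything after a second dose is absent, including the period after an active second dose, when a subject on 200 mg can have taken 400 mg within 24 hours. Part of the follow-up of the first dose also goes: a subject who redoses at 3 hours and has an event starting at 5 hours is not counted in this table. Under SAP 5, percentages use the number of subjects in the summarised population, so that subject stays in the denominator.

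A statement about safety in patients with risk factors that relied on this table would describe one dose, with shortened follow-up in redosers, in a trial that allows two.

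**Working it through.** **Is the table planned anywhere else?** The adverse event outputs named in SAP 11.8, by subgroup:

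| SAP section | Subgroup | TEAE incidence, Safety | TEAE incidence, Safety-2nd Dose |
|---|---|---|---|
| 11.8.1 | Triptan use within three months of screening | yes | no |
| 11.8.2 | Dosed more than 4 h after migraine start | no | no |
| 11.8.3 | Topamax or propranolol | no | no |
| 11.8.4 | Topamax | yes | yes |
| 11.8.5 | Propranolol | yes | yes |
| 11.8.6 | One or more cardiovascular risk factors | yes | no |
| 11.8.7 | Dizziness as a TEAE | dizziness timing only | dizziness timing only |

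The other sections do not fill the gap. SAP 12.1 displays adverse events by treatment group and overall. Protocol 10.8.1 splits them by arm, sequence and dose. SAP 8.1 summarises risk factors in the Safety-2nd Dose population, but as a baseline characteristic. SAP 13 reports resource use by sequence. None tabulates adverse events after a second dose by risk-factor status.

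**How much of a redoser's follow-up does the table hold?** Inputs:

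- Second dose at time t after the first. SAP 4.1 defines rescue subjects as those who "took a second dose of study drug between 2 hours and 24 hours post first dose"; recurrence dosing is also allowed up to 24 h.
- An event starting or worsening at or "within 48 hours after the time of dosing with study drug will be considered a TEAE" (SAP 12.1).

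For t up to 48 h, the treatment-emergent period of a subject with two doses runs from 0 to t + 48 h, and the table keeps 0 to t. The share kept is t / (t + 48):

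- t = 2 h: 2 / 50 = 4.0%
- t = 24 h: 24 / 72 = 33.3%

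A subject who does not redose contributes the full 48 h.

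**How many subjects?** The documents give neither redosing uptake nor the share with a risk factor. As an illustration only, assume 30% to 50% uptake and 40% to 70% with at least one risk factor, independent of each other, in an arm of 570. The sequence table (Protocol 5.5.1) lists the active second dose twice for each placebo second dose, which reads as 2:1.

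- Active then active: 570 × 2/3 = 380. The range is 380 × 0.3 × 0.4 = 46 to 380 × 0.5 × 0.7 = 133 per lasmiditan arm.
- Active then placebo: 570 × 1/3 = 190. The range is 190 × 0.3 × 0.4 = 23 to 190 × 0.5 × 0.7 = 67.

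**What would the added table show?** For the active-active groups of 46 and 133:

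- 95% half-width at 50% incidence, 1.96 × √(0.25/n): 14.4 points and 8.5 points.
- One-sided 95% upper bound with zero events, 1 − 0.05^(1/n): 6.3% and 2.2%.

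That is enough to describe common events, but not to exclude rare cardiac ones.

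**The case against.** The strongest reply is that no document requires this table. The safety objective names no subgroup, and the overall Safety-2nd Dose tables satisfy it. The statement about patients with risk factors is introductory text, not an objective. SAP 5.1 presents the subgroup analyses as additions to the protocol, and SAP 4.3 warns that the study was not designed for high power within subgroups. No uniform rule is broken either, since only two of the seven subgroups get the second-dose incidence table. Protocol 10 allows further exploratory analyses. All adverse events are listed by subject, so a determined reader could count them.

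Much of this stands as a limit on importance. The table is optional and descriptive, and it would not settle rare events. Redosers are selected by their response to the first dose, so comparing sequences is not a clean randomised contrast. The 4% to 33% is a share of time, not of events missed, and it applies to the permitted window; SAP 5.4 foresees some second doses after 24 h, for which the share would be higher (48 / 96 = 50% at 48 h).

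None of it supplies the table. A general allowance for exploratory work does not plan this output, and counting from listings is not a tabulated incidence. Where the authors wanted a second-dose subgroup table they named it, and SAP 5.1 gives no reason for omitting it here. The protocol makes a specific safety statement about risk-factor subjects; it makes none about the triptan subgroup, which has the same omission.

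**Conclusion.** The concern holds. Followed as written, the plan gives one adverse event table for subjects with cardiovascular risk factors. For anyone who redoses in the permitted window, it holds only 4% to 33% of the treatment-emergent period. That range follows from the documents' own dosing and event windows. The number of subjects affected does not: 46 to 133 per lasmiditan arm on two active doses, plus 23 to 67 on active then placebo, rests on assumed uptake and risk-factor prevalence.

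This is a reporting gap to consider, not a threat to the trial. Serious or cardiac events after redosing would still show in the overall tables and listings. What is missing is their incidence in the group for which the protocol says safety will be confirmed.

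**What to change.** In SAP 11.8.6, add "Incidence of Treatment-Emergent Adverse Events for Safety-2nd Dose population", presented by treatment sequence and labelled descriptive, as in 11.8.4 and 11.8.5. Base any statement on safety in patients with cardiovascular risk factors on the first-dose and second-dose tables together, and state that the first-dose table ends follow-up at redosing.

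The cost is one more run of a table program already planned for two other subgroups. The risk-factor flag is needed anyway for the existing 11.8.6 table, and the Safety-2nd Dose population is a subset of the Safety population, so no new data are needed. No confirmatory analysis changes. Specifying the table before unblinding is cleaner than adding it afterwards.

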12 SAFETY ANALYSIS

This section details the specifications for summarizing safety endpoints.

Adverse event analyses will be presented on both the Safety and Safety-2nd Dose populations. Summaries on the Safety population will only include data up to the time of dosing with a second dose, and will be presented based on the first dose taken. Summaries on the Safety-2nd Dose population will only include data on or after the time of dosing with a second dose, and will be presented based on treatment sequence.

Laboratory, vitals, ECG, and C-SSRS analyses will be presented on the Safety population. These analyses will be presented by treatment sequence.

Safety endpoints will be summarized using descriptive or counts and percentages, as appropriate.

Values for all safety endpoints will also be presented in listings sorted by treatment group, site, and subject.

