5.2 Analysis of First and Second Doses

Any analyses based on first dose will only include data observed up to the time of dosing with a second dose. These summaries will be presented based on the first dose taken. The exception to this is the primary and secondary endpoints at the 2-hour time point; if a second dose is taken before the 2-hour time point, the subject will still be included in the summary at 2 hours and will be analysed as having not achieved headache pain-free or MBS-free status at 2 hours.

Any analyses based on the second dose will only include data observed on or after the time of dosing with a second dose. These summaries will be presented by treatment sequence, listed in Section 2.3. Analyses based on the second dose will be done for both the rescue and recurrence subpopulations.

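### The first-dose adverse event tables stop at the second dose, and no planned table gives any-TEAE or any-serious-TEAE incidence per first-dose arm over the whole treated attack

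*SAP*

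**What the plan says.** SAP Section 12 divides the adverse event analysis at the second dose. For the first part: "Summaries on the Safety population will only include data up to the time of dosing with a second dose". These tables are grouped by the first dose taken. For the second part: "Summaries on the Safety-2nd Dose population will only include data on or after the time of dosing with a second dose". These are grouped by treatment sequence. Section 5.2 states the same cut for every first-dose analysis and exempts only the 2-hour primary and secondary efficacy endpoints.

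Section 12.1 sets the window: an event that starts or worsens "at or within 48 hours after the time of dosing with study drug will be considered a TEAE". Section 4.1 defines rescue users as "subjects who did not achieve headache pain-free at 2 hours, completed the 2-hour assessments", who "took a second dose of study drug between 2 hours and 24 hours post first dose". Recurrence users were pain-free at 2 hours and then had pain return. Section 5 takes percentages over all subjects of the summarised population in each group. No adjustment for length of follow-up is described.

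The tables listed in Section 12.1 (overall summary, TEAEs, relationship, severity, discontinuation, serious events, deaths) all fall under the split. Section 12.1 also says that "frequencies of adverse events will be displayed by applicable treatment group and overall". There, 'overall' most naturally means all treatment groups together, not both dosing periods together.

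**The concern.** A subject who takes a second dose at, say, 3 hours contributes 3 hours to the first-dose table. A subject who does not contributes 48. Both count fully in the denominator. Whether the cut happens depends mainly on not being pain-free at 2 hours, which is the outcome that treatment is meant to change. The first-dose percentages are therefore incidences up to the second dose, with response-dependent follow-up, and nothing in the SAP asks for them to be labelled so.

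Events after the second dose, including serious TEAEs and deaths, appear only by sequence among subjects who chose to re-dose. A basic tolerability question then has no table: of the subjects who started the attack on a given treatment, what share had any TEAE, or any serious TEAE, by the end of that attack?

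**Working it through.** **Plan's own figures.** The documents give no figure for second-dose uptake, safety follow-up or total TEAE incidence, so there is none to reproduce. The pain-free rates used below come from SAP 2.2: 7.4% placebo, 13.9% for 50 mg, 13.6% for 100 mg, 18.8% for 200 mg. With 570 per arm and one-sided 0.025, the normal approximation gives power of 94.6% (50 mg), 92.8% (100 mg) and over 99.9% (200 mg). This agrees with the stated >90%.

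**Step 1: who can take a rescue dose.** Share not pain-free = 1 − pain-free rate.
- Placebo: 1 − 0.074 = 92.6% (528 of 570)
- 50 mg: 86.1% (491)
- 100 mg: 86.4% (492)
- 200 mg: 1 − 0.188 = 81.2% (463)

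**Step 2: is the second dose mostly for non-response?** Let p be the pain-free rate, u the uptake among non-responders and r the re-dosing rate among responders. Rescue share = u(1 − p) / [u(1 − p) + rp]. With u from 30% to 70% and r from 10% to 100% (both assumed), it runs from 0.2436 / (0.2436 + 0.188) = 56% (200 mg, u = 30%, r = 100%) to 0.6482 / (0.6482 + 0.0074) = 99% (placebo, u = 70%, r = 10%). So yes, over that range.

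**Step 3: mean first-dose window.** Hours = 48 − u(1 − p)(48 − t) − 0.2p(48 − 12). Assumptions: rescue dose at t = 2, 4 or 12 h; 20% of responders re-dose at 12 h; equal uptake across arms. For u = 50% and t = 4:
- Placebo: 48 − 0.463 × 44 − 0.0148 × 36 = 27.1 h
- 200 mg: 48 − 0.406 × 44 − 0.0376 × 36 = 28.8 h

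Over u = 30% to 70% and all three values of t, the mean is 17.6 to 37.5 h on placebo and 20.5 to 37.9 h on 200 mg. The gap is 0.4 to 2.9 h.

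**Step 4: direction of the gap.** If uptake differs by arm, rescue use is equal when uptake among 200 mg non-responders is 0.926 / 0.812 = 1.14 times that on placebo. Above that ratio, 200 mg is cut more. Counting recurrence doses lowers the threshold, because 200 mg has more responders.

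**Step 5: events that leave the first-dose table.** Protocol 4.2 gives Phase 2 TEAE rates of 22% (placebo) and 86% (200 mg). Treat these as full-window rates. Assume exponential onset with mean m, rescue dose at 3 h and 20% recurrence use at 12 h. Let F(x) = (1 − e^(−x/m)) / (1 − e^(−48/m)). Incidence shown = rate × [1 − u(1 − p)(1 − F(3)) − 0.2p(1 − F(12))].

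| Mean onset | Uptake | Placebo (full 22%) | 200 mg (full 86%) |
|---|---|---|---|
| 1 h | 30% | 21.7% | 85.0% |
| 1 h | 50% | 21.5% | 84.3% |
| 1 h | 70% | 21.3% | 83.6% |
| 4 h | 30% | 19.1% | 75.9% |
| 4 h | 50% | 17.2% | 69.3% |
| 4 h | 70% | 15.2% | 62.7% |
| 12 h | 30% | 17.1% | 68.6% |
| 12 h | 50% | 14.0% | 57.8% |
| 12 h | 70% | 10.8% | 47.0% |

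The relative loss is 1.4% to 50.7% on placebo and 1.2% to 45.4% on 200 mg. These are illustrations under assumed inputs, not forecasts.

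**Step 6: can the total be rebuilt?** Suppose A subjects in a first-dose arm have a TEAE before the second dose and B have one from then on (sequences summed). One subject can be in both counts, so the number with any TEAE is only known to lie between max(A, B) and A + B.

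**The case against.** The strongest reply is that the split is what the protocol asks for. Protocol 5.4 states the safety objective for each dose as a first dose and as a second dose, and Protocol 10.8.1 plans the tables by arm, sequence and dose. For the question of what follows one dose before more drug is taken, stopping at the second dose is reasonable. This stands, and the SAP does not depart from the protocol here.

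A reader might also infer that events are lost. They are not: later events are tabulated by sequence, and all safety values are listed. The second dose is randomised after a lasmiditan first dose, so the lasmiditan-then-placebo sequence gives some view of late first-dose effects. Laboratory, vital sign, ECG and C-SSRS analyses carry no stated cut.

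A third reading is that the cut biases the comparison between arms. The documents do not support that. They give no uptake; under equal uptake the gap is at most about 3 of 48 hours, and modest differences in uptake would reverse it. If onset is quick, as Protocol 4.2 reports for intravenous dosing, few events move at all.

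Finally, a pooled table mixes one-dose and two-dose exposure: a second dose after lasmiditan may be active or placebo, and after placebo it is always placebo. That is a sound reason not to let it replace the split tables. None of these replies supplies the missing per-arm total.

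**Conclusion.** The point holds as a reporting gap. Two things follow from the SAP text alone: the first-dose table is an incidence up to the second dose, and no planned table gives any-TEAE or any-serious-TEAE incidence per first-dose arm over the treated attack. The two planned tables do not determine that incidence; it would have to be counted from listings or subject-level data.

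The first-dose table counts fewer events than a full 48-hour window would in any arm where second doses are used and some subjects have their first event after re-dosing. The size rests on uptake and onset, both assumed here: about 1% to 3% of TEAEs with 1-hour mean onset, and up to about half with 12-hour mean onset and 70% uptake. It would go too far to say that incidence is wrongly understated in every arm, because that presumes the 48-hour target rather than the by-dose one. 'First-dose arm' here means the treatment taken, since the Safety population is grouped by drug used where that differs from the assignment.

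**What to change.** - Keep both planned sets of tables as the by-dose analyses that the protocol specifies.
- Label the first-dose tables as cut at the second dose.
- Add a table of TEAEs (any, related, severe, serious, leading to discontinuation, leading to death) from first dose to 48 hours after the last dose, for all Safety subjects, by first-dose treatment received and by sequence.
- Footnote that it mixes one-dose and two-dose exposure and that observation runs from 48 hours to as much as 72 hours (24 + 48) for a second dose taken within the allowed time. It supplements the split tables and does not become the headline.
- Report second-dose uptake and timing by first-dose arm beside it. SAP Section 6 already counts second-dose users by sequence and Section 10 summarises time between doses, so this mostly means regrouping planned output.

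The cost is a few extra table shells from data already collected. No endpoint or test changes. The added table will show somewhat higher incidences than the cut one.

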#### Safety:

Adverse events will be summarized, and event rates will be presented by treatment arm and dose (initial dose and second dose for rescue or recurrence or use of alternative rescue medication). Physical examinations, vital signs, ECG parameters and clinical laboratory data, will be summarized by treatment arm and dose in terms of change from baseline status.

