#### **10.8.2 Physical Examinations, Vital Signs, ECG Parameters and Clinical Laboratory Test Values,**

By-subject listings of physical examinations, vital signs, ECG parameters and clinical laboratory data will include indications of values that are outside the reference ranges, and values that are clinically significant. Shift tables describing out-of-reference range shifts will be provided for vital signs, ECGs and clinical laboratory test results from the **Screening/Visit 1** to **EoS/Visit 2**, as appropriate by treatment arm and dose.

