4 ANALYSIS POPULATIONS

The following analysis populations will be defined for this study. Subjects' inclusion in or exclusion from these analysis populations will be finalized prior to study unblinding

Randomized population	All randomized subjects. Subjects will be evaluated by the drug to which they are randomized.
Safety population	All randomized subjects who use at least one dose of study drug, regardless of whether or not they undergo any study assessments. Subjects will be evaluated by the drug they use, not by the drug to which they are randomized, when data indicate a difference.
ITT population	All randomized subjects who use at least one dose of study drug and have any post-dose headache severity or symptom assessments. Subjects are evaluated by the drug to which they are randomized.
mITT population	All ITT subjects who treat a migraine attack within four hours of onset. Subjects will be evaluated by the drug to which they are randomized. The mITT population is the primary analysis population.
PP population	All mITT subjects will be considered per protocol (PP) if they do not have major protocol deviations, enumerated below, which might impact the assessment of efficacy. Subjects will be evaluated by the drug to which they are randomized.

Safety-2nd Dose population	All randomized subjects who were considered in the safety population after the first dose and use a second dose of study drug, regardless of whether or not they undergo any study assessments. Subjects will be evaluated by the drug they use, not by the drug to which they are randomized.
ITT-2nd Dose population	All randomized subjects who were considered ITT after the first dose and use a second dose of study drug and have any post-dose headache severity or symptom assessments. Subjects will be evaluated by the drug to which they are randomized.

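### Laboratory, vital-sign and ECG tables by treatment sequence pool subjects who took one dose with those who took two, and no planned table separates them

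*SAP*

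**What the plan says.** SAP section 12 sets the population and the columns for these data: "Laboratory, vitals, ECG, and C-SSRS analyses will be presented on the Safety population. These analyses will be presented by treatment sequence". SAP section 4 defines the Safety population as "All randomized subjects who use at least one dose of study drug, regardless of whether or not they undergo any study assessments", so a second dose is not needed for entry. It adds an as-treated rule: "Subjects will be evaluated by the drug they use, not by the drug to which they are randomized, when data indicate a difference".

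The term treatment sequence is fixed by SAP 5.2, on second-dose analyses: "These summaries will be presented by treatment sequence, listed in Section 2.3". SAP 2.3 lists seven randomised pairs of first and second dose, the second to be taken only if needed. SAP 12.2 to 12.4 add no split by whether it was taken.

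The protocol is organised differently. The synopsis says that physical examination, vital-sign, ECG and laboratory data "will be summarized by treatment arm and dose in terms of change from baseline status". Protocol 10.8.2 asks for shift tables "as appropriate by treatment arm and dose". Protocol 10.8 spells out dose as first dose, second dose for rescue or recurrence, or alternative rescue medication.

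**The concern.** The protocol's safety objective (section 5.4) covers lasmiditan both as a first and as a second dose, and names vital signs, laboratory tests and ECGs among the measures. Two descriptive questions follow: what is seen after one dose, and what a second active dose adds.

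The planned layout answers neither cleanly. A subject assigned 200 mg/200 mg who needed only the first dose sits beside subjects who took 400 mg in total within 24 hours. A subject assigned 200 mg/placebo who took only the first dose had the same exposure but appears in another column. The same holds at 50 mg and 100 mg.

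What is at stake is the visibility of a second-dose effect in mean changes, ECG shifts and the QTc change categories of SAP 12.4. Efficacy conclusions are not touched.

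**Working it through.** The plan gives no figure to reproduce here, so the check is first one of text and then one of direction and illustrative size.

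**Text, side by side**

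1. Population: one dose suffices (SAP 4).
2. Columns: the seven sequences of SAP 2.3, none of which means no second dose taken.
3. As-treated rule (SAP 4): it moves a subject whose drug used differs from the drug assigned. It does not say where a subject with no second dose goes, and no column exists for one.
4. Adverse events, also in SAP 12: Safety-population summaries stop at the second dose, and Safety-2nd Dose summaries start there. The doses are separated for adverse events but not for laboratory, vital-sign or ECG data.
5. Protocol 10.8, 10.8.2 and synopsis: treatment arm and dose.
6. Protocol section 10 says that changes to analysis methods that need no amendment will be described and justified in the SAP. SAP 5.1 lists several changes, but not this one.

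**Dilution**

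Let f be the fraction of the 200 mg/200 mg column who took the second dose, b the outlier rate after one dose and r the rate after two. The column shows (1 − f)b + f·r = b + f(r − b). For a mean shift, an added effect d appears as f·d.

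f, b and r are all assumptions; the documents give none of them. With r = 2%:

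| f | b = 1% | b = 0.5% |
|---|---|---|
| 20% | 1 + 0.2 × 1 = 1.2% | 0.5 + 0.2 × 1.5 = 0.8% |
| 40% | 1 + 0.4 × 1 = 1.4% | 0.5 + 0.4 × 1.5 = 1.1% |
| 60% | 1 + 0.6 × 1 = 1.6% | 0.5 + 0.6 × 1.5 = 1.4% |

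**Column make-up**

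SAP 2.1 plans 570 treated subjects per first-dose group. The active second dose occupies two of the three rows for each lasmiditan dose in SAP 2.3. Reading this as a 2:1 allocation (an inference, since the ratio is not stated) gives 570 × 2/3 = 380 on 200 mg/200 mg and 570 × 1/3 = 190 on 200 mg/placebo. At f = 20%, 40% or 60%, 76, 152 or 228 of the 380 took two active doses, so 80%, 60% or 40% of the column had 200 mg only.

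**Is a smaller but cleaner comparison better?**

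Compare 200 mg/200 mg with 200 mg/placebo, with the same f in both columns and f unrelated to the effect. With the standard deviation set to 1, the expected z is f·d/√(1/380 + 1/190) for whole columns and √f·d/√(1/380 + 1/190) among takers only. Restricting to takers raises it by 1/√f, which is 1.58 at f = 0.4. Taking d = 0.288 SD, chosen to give 90% power (two-sided 0.05) if everyone took the second dose:

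| f | whole columns | takers only |
|---|---|---|
| 60% | 49.4% | 70.9% |
| 40% | 25.4% | 53.6% |
| 20% | 9.5% | 30.5% |

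No such test is planned. The figures show only that separating takers gains more than the smaller numbers lose.

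**The case against.** The best defence has four parts.

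- The protocol wording is qualified by where appropriate and as appropriate, and these summaries are descriptive. All safety values are listed, and SAP 6 counts second-dose takers by sequence. That is true, but neither listings nor disposition counts summarise results by dose received.
- Laboratory tests, vital signs and ECG have one scheduled post-dose assessment, at Visit 2, within 7 days of treatment. A subject who took both doses has no separate first-dose measurement, and an acute effect may have passed. This stands in full: a reader might infer that the layout is what would hide an acute effect, but visit timing limits detection under any layout.
- Protocol 4.2 reports a negative thorough QT study at 400 mg, and 4.3 reports no clinically significant vital-sign, ECG or laboratory effects at oral doses up to 400 mg. This lowers the stakes. It does not replace reporting in a trial that admits patients with cardiovascular risk factors.
- The sequence tables preserve a randomised comparison. This also stands, and is why they should be kept.

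Three stronger readings are tempting but unsupported. One is that a 2% two-dose outlier rate would show as 0.4%, 0.8% or 1.2%; that needs a single-dose rate of exactly zero. Another is that the Safety-2nd Dose population serves adverse events alone; SAP 6, 8.1 and 8.3 also use it, for disposition, demographics and medical history. What is missing is a laboratory, vital-sign or ECG table on it. The third is that the SAP ignores the drug actually used; its as-treated rule says otherwise, but leaves subjects without a second dose unplaced. C-SSRS, named in the same sentence, is only listed (SAP 12.6), so dilution does not arise.

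**Conclusion.** The point holds as a reporting defect that is cheap to correct. The direction is certain whenever some subjects skip the second dose: the sequence column shows only the fraction f of any added effect of a second active dose. The size cannot be computed from the documents. The 1.2% to 1.6% illustration rests on assumed rates of 1% and 2% and assumed uptake of 20% to 60%. The 380 and 190 rest on the inferred 2:1 split, and the power figures also on a chosen effect of 0.288 SD.

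The departure from the protocol's organisation by arm and dose, and its absence from SAP 5.1, rest on the text alone. The documents do not support any inference that a safety signal exists or would be concealed.

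**What to change.** In SAP 12 and 12.2 to 12.4, keep the tables by treatment sequence and add two sets:

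1. By first dose received, all Safety subjects, with those who took only the first dose shown separately from those who took two.
2. On the Safety-2nd Dose population, by treatment sequence, so that active and placebo second doses, which were randomised, are compared among takers within each first-dose group.

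Label any comparison of takers with non-takers as descriptive, because taking the second dose is the subject's choice. State in SAP 4 where a subject with no second dose is placed under the as-treated rule. Record and justify the departure from the protocol in SAP 5.1.

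The cost is SAP wording and table shells; dosing data are already collected in the e-diary and CRF. The drawbacks are more columns, second-dose groups that are smaller and self-selected, and the limit set by a single post-dose visit, which remains.
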